## 9.9 Safety Monitoring

An investigator or designee will perform the infusions and will be present at least 1 hour after the completion of the infusions. Thereafter, the investigator will remain on site and be available by telephone for prompt response, if needed, for at least 4 hours post-infusion. If a participant demonstrates a significant adverse reaction to cocaine, the cocaine administration will be halted, appropriate medical response will be implemented per site's standard operating procedures, and the participant will be discontinued from the remainder of the study.

Emergency medical coverage at the clinical research unit will be available to the participants. The clinical site will provide emergency medical coverage and services to manage potentially serious and life-threatening medical emergencies should they arise at any point during the clinical trial. Advanced Cardiovascular Life Support (ACLS) trained personnel, including but not limited to physicians and paramedics, will be available at all times during the inpatient component of this clinical trial. Further, an investigator's presence will be required at all times during and immediately after cocaine infusions to ensure additional safety. An investigator will be present on-site during and for at least 1 hour after infusion and will be on site for at least 4 hours after completion of the infusion. Completely equipped and regularly monitored crash carts will be readily available should they be required at any point. Also, the study site will be located in close proximity to a major medical center.

## 9.10 Individual Participant Stopping Criteria

Further participation of the participant in the study is stopped if any of the following criteria are met:

1. Acute chest pain
2. Systolic BP > 160 mmHg sustained for 5 minutes or more
3. Diastolic BP < 40 mmHg or > 100 mmHg sustained for 5 minutes or more
4. Heart rate < 40 bpm or > 160 bpm sustained for 5 minutes or more
5. QTcF  $\geq$  500 msec, or uncorrected QT interval > 600 msec
6. Clinically significant ECG changes in the opinion of an investigator
7. AST > 2 ULN
8. ALT > 2 ULN
9. BUN > 2 ULN
10. Creatinine > 1.5 mg/dL
11. Significant neurological or psychiatric events (*e.g.*, psychosis) or any behavioral manifestations of cocaine toxicity
12. Any condition that in the clinical judgment of an investigator is of sufficient magnitude to present a danger to the participant
13. Participant experiences an SAE that is not clearly unrelated to study drug or cocaine

NIDA and Promentis Pharmaceuticals Inc. alone may suspend dosing at any time for any safety reason. Factors that must be considered for suspension of dosing include the frequency, severity, clinical significance, possible causality, and anticipated reversibility of all observed AEs or laboratory abnormalities. The IRB will be notified if dosing is suspended.

### 9.11 Participant Discontinuation

Participants will be excluded or discharged if their behavior is disruptive, non-compliant with study procedures, or otherwise not in compliance with remaining on the Unit.

Study participants can withdraw from the study at any time for any reason. Subjects can be discontinued if they withdraw consent, are unable to remain under medical supervision, are noncompliant or have a major deviation from the protocol, pregnancy, experience an SAE or severe AE, if the site PI feels that continuation would not be in the best interest of the subjects, or if the trial is discontinued. If discharged from the clinic early, all assessments scheduled for Day 11 will be performed.

### 9.12 Study Stopping Criteria

The study will be halted from further enrollment if any of the following criteria are met at any point during the study:

- Four participants experience a severe AE, such as significant neurological or psychiatric events (*e.g.*, psychosis) or behavioral manifestations of cocaine toxicity
- Two participants experience a similar SAE that is not clearly unrelated to study drug or cocaine
- Two severe AEs related to cocaine toxicity
- Two participants fulfill the following ECG criteria based on the mean of triplicate measures ( $\geq 1$  minute apart), that will be completed once the first ECG demonstrates a prolonged interval: QTcF  $\geq 500$  msec or uncorrected QT interval of  $>600$  msec.

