each session. The participants will receive either SXC-2023 800 mg or matched placebo once a day every morning from Days 3 to 9. On Day 8, participants will receive cocaine 20 mg infusion (Infusion Session 4) and on Day 9 will receive cocaine 40 mg (Infusion Session 5). Each cocaine infusion will be preceded or followed by saline i.v. infusion. The first infusion on Days 8 and 9 will begin approximately 3 hours after SXC-2023 or placebo. Each infusion will consist of a 2 mL i.v. push and will be administered 60 minutes apart. The order of the saline and cocaine infusions for each participant for Infusion Sessions 4 and 5 will be the same as the randomized order for Infusion Sessions 2 and 3, respectively. The participants will be discharged from the research clinic on Day 11, 2 days after the last infusion of cocaine (Infusion Session 5), and will have a telephone follow-up call between 7 and 10 days after clinic discharge.

The study schema is illustrated in [Figure 1](#) and the schedule of infusion sessions is shown in [Table 1](#).

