## 11.3 IRB Approval

Prior to initiating the study, the Principal Investigator will obtain written approval from the IRB of record to conduct the study. Should changes to the study protocol become necessary, protocol amendments will be submitted in writing to the local IRB by the site Principal Investigator for IRB approval prior to implementation. In addition, NIDA and the local IRB will approve all advertising materials used for participant recruitment and any educational materials given to the

participant. Progress reports will be submitted to the local IRB annually or at a frequency requested by the IRB. The Investigator will report to the IRB all changes in research activity and all unanticipated problems involving risks to human participants or others.

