#### 11.5 Outside Monitoring

**Medical Monitor:** A medical monitor has been appointed for the study. The medical monitor will be available for making recommendations to the Investigator and the Sponsor on the severity of any SAEs, the relatedness to the study interventions, and for determining if the SAE should be reported to the FDA in a 7 or 15 day expedited report or an annual report. The medical monitor will also be responsible for tracking and assessing trends in the AEs reported. In the event that the medical monitor and Investigator do not concur on SAE evaluations, both opinions will be reported to the FDA.

**Clinical Monitors:** All Investigators will allow representatives of the Sponsor to periodically monitor, at mutually convenient times during and after the study, all CRFs and corresponding source documents for each participant. These monitoring visits provide the Sponsor with the opportunity to evaluate the progress of the study and to inform the Sponsor of potential problems. The monitors will assure that submitted data are accurate and in agreement with source documentation; verify that the investigational product is properly stored and accounted for, verify that participants' consent for study participation has been properly obtained and documented, confirm that research participants entered into the study meet inclusion and exclusion criteria, and assure that all essential documentation required by GCP guidelines are appropriately filed.

Monitors will conduct a study initiation visit prior to the start of the study. At this visit, they will assure that proper study-related documentation exists, assist in training Investigators and other site personnel in study procedures and GCP guidelines, confirm receipt of study supplies, and assure that acceptable facilities and staff are available to conduct the study.

Routine monitoring visits by NIDA's representatives will be scheduled at appropriate intervals but probably more frequently at the beginning of the study. At these visits, the monitors will

verify that study procedures are being conducted according to the protocol guidelines and will review AEs and SAEs and drug accountability. At the end of the study, they will advise on storage of study records and return of unused investigational products. All sites should anticipate visits by NIDA and the FDA.

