## **E. SERIOUS ADVERSE EVENT AND UNEXPECTED ADVERSE EVENT REPORTING**

### ***24 hour Reporting Requirements***

Any serious adverse event, including death due to any cause, which occurs to any participant from the time of admission through discharge whether or not related to the investigational product, must be reported within 24 hours to the NIDA Medical Monitor and the NIDA Project Officer via email.

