### ***Reporting to the FDA***

The IND Sponsor is required to report SAEs to the FDA:

- in **7 days** if the SAE is unexpected (or, if expected, unusually serious or rarely seen), life-threatening or lethal, and at least possibly related to the investigational product, with a follow-up written report in 8 days;
- in **15 days** if the SAE is unexpected (or, if expected, unusually serious or rarely seen), but not immediately life-threatening;
- in an annual report in all other cases.

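### A study-level safety trigger stops enrolment only; nothing requires a dosing decision for participants already in house, including before the combined SXC-2023/cocaine sessions on Days 8 and 9

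*Protocol*

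**What the plan says.** Protocol 9.12 lists four study-level criteria: four participants with a severe AE; two similar SAEs not clearly unrelated to study drug or cocaine; "Two severe AEs related to cocaine toxicity"; and two participants with a confirmed QTcF of at least 500 msec or QT above 600 msec. The stated action for all four is "The study will be halted from further enrollment if any of the following criteria are met at any point during the study". SAP 4.4.1 uses the same sentence.

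The schedule in Protocol 6 places randomisation on Day -1, cocaine-only baseline sessions on Days 1 and 2, daily SXC-2023 or placebo on Days 3 to 9, and then the sessions on treatment: "On Day 8, participants will receive cocaine 20 mg infusion (Infusion Session 4) and on Day 9 will receive cocaine 40 mg".

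Other provisions also bear on safety:
- Protocol 9.10, after the individual stopping criteria (and SAP 4.4.2): "NIDA and Promentis Pharmaceuticals Inc. alone may suspend dosing at any time for any safety reason". It lists factors to weigh and requires IRB notification if dosing is suspended.
- Protocol 11.5: "The medical monitor will also be responsible for tracking and assessing trends in the AEs reported".
- Protocol 11.3: the investigator reports to the IRB "all changes in research activity and all unanticipated problems involving risks to human participants or others".
- Protocol Appendix B, part E: a serious event "must be reported within 24 hours to the NIDA Medical Monitor and the NIDA Project Officer via email". The same part covers unexpected AEs, with supporting documents due within 3 days, and adds that "The IND Sponsor is required to report SAEs to the FDA".

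**The concern.** A participant who personally reaches a limit is in most cases already stopped under Protocol 9.9 or 9.10. What a study-level criterion adds is evidence of a pattern across participants. The people to whom that evidence matters most are those in house who have yet to receive cocaine together with SXC-2023, since that interaction is the primary safety question. An enrolment halt does not reach them. A site following 9.12 to the letter would stop enrolling and carry on with the remaining infusions. Whether it should do so is left to a power that no trigger requires anyone to use or document.

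**Working it through.** The plan gives no figure on this point and no power or error-rate calculation applies. The check is a count from the infusion schedule and a side-by-side reading of the provisions.

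**1. What an enrolment halt leaves in place.** Inputs: Protocol 6, Table 1 and 9.4. Doses by session are 20 mg then 40 mg (Session 1, Day -2), 20 mg (Session 2, Day 1), 40 mg (Session 3, Day 2), 20 mg (Session 4, Day 8) and 40 mg (Session 5, Day 9).

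| Position when a criterion is met | Cocaine infusions ahead | Cocaine ahead | Of these, on SXC-2023/placebo |
|---|---|---|---|
| In house, awaiting Session 1 | 2 | 20 + 40 = 60 mg | 0 |
| Randomised, before Session 2 | 4 | 20 + 40 + 20 + 40 = 120 mg | 2 |
| Between Sessions 2 and 3 | 3 | 40 + 20 + 40 = 100 mg | 2 |
| Between Sessions 3 and 4 | 2 | 20 + 40 = 60 mg | 2 |
| Between Sessions 4 and 5 | 1 | 40 mg | 1 |

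The first row counts screening infusions only. Enrolment follows Session 1 under 9.4, so a halt read literally blocks randomisation but does not clearly stop those two infusions. Once the twentieth participant has been randomised, the halt affects only possible replacements.

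**2. Does any provision force a decision for the other participants?**

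| Provision | Acts on | Nature | Dosing decision for the others required? |
|---|---|---|---|
| 9.9 significant reaction to cocaine | affected participant | mandatory | No |
| 9.10 criteria (ECG limits, neurological or psychiatric events, cocaine toxicity, investigator-judged danger, SAE) | affected participant | mandatory | No |
| 9.10 / SAP 4.4.2 suspension of dosing | whole trial | discretionary | No; factors are listed, but no event starts the weighing |
| 9.11 discontinuation | individual, or all if the trial is discontinued | permissive | No; no text says a 9.12 criterion discontinues the trial |
| 11.5 medical monitor | whole trial | duty to track trends | No |
| 11.3 IRB reporting | whole trial | mandatory, no time limit | No; it is a report |
| Appendix B reporting | SAEs and unexpected AEs | mandatory, timed | No; it is a report |

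**3. Can a criterion be met outside the timed reporting route?** Three of the four criteria do not require an SAE: the four severe AEs, the two severe AEs related to cocaine toxicity, and the ECG criterion. Appendix B also covers unexpected AEs, and Protocol 11.7 allows important medical events to be classed as serious. So the timed route is avoided only where the events are both expected and judged non-serious.

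**4. What a 24-hour hold would cost.** Sessions fall on Days 1, 2, 8 and 9. If sessions start at the same clock time (an assumption), consecutive starts are 24 hours apart, so a 24-hour hold catches at most one per participant. From Session 3 on Day 2 to 24 hours before Session 4 on Day 7, that is for 7 − 2 = 5 days, it catches none. The completer margin is 10 randomised − 8 required = 2 per group.

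**The case against.** The strongest reply is that the sponsor would review dosing anyway and has every means to do so. The suspension clause applies at any time, and its factors include the frequency of all observed events, so it is a trial-level tool despite sitting in the individual section. An enrolment halt is itself a change in research activity, so an IRB report would follow under 11.3. Participants who show toxicity are removed under 9.9 and 9.10. All of this stands. It rules out a stronger reading that a reader might infer, namely that dosing cannot be stopped, that participants are unmonitored, or that non-serious triggers go unreported. The documents support none of these. What the reply does not supply is a required, recorded decision before the next infusion.

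The heading of 9.12 might also be read to mean that the whole study stops. Its operative sentence limits the action to enrolment.

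A second reply is that a hold may be set off by events that say nothing about the combination, since the first criterion requires no link to study drug. That is true, and it is why the remedy must allow a prompt decision to continue. That option cannot rest on the affected participant having received placebo, because using it would unblind the sponsor and manufacturer in a 20-person double-blind trial.

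A third is that the choice between holding cocaine alone and holding both drugs is a judgement. That also stands, so the decision should cover both.

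**Conclusion.** The point holds in a narrow form. When a 9.12 criterion is met, the only required action is to stop enrolling, while a randomised participant may still have up to four cocaine infusions (120 mg) ahead, two of them on top of SXC-2023 or placebo. No provision in either document requires a suspend-or-continue decision for those participants.

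The count rests on the published schedule alone. The documents state neither how many participants are in house at once nor the expected event rate, so the number exposed at a trigger and any risk of harm cannot be computed. A reader might infer that the plan exposes participants to a quantifiable excess risk; the documents do not support that. This is an inexpensive improvement to participant safety. It does not affect the validity of the analysis.

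**What to change.** Amend Protocol 9.12, and SAP 4.4.1 only to keep the wording consistent, to state that when any criterion is met:

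- Enrolment stops, and no participant in house, including anyone awaiting screening Session 1, receives a further cocaine infusion until NIDA and the manufacturer, advised by the medical monitor, have documented a suspend-or-continue decision.
- The decision covers both cocaine and SXC-2023/placebo, uses the factors already listed in 9.10, is made on blinded data, and is targeted within 24 hours and before the next scheduled session.
- Daily SXC-2023/placebo continues meanwhile unless they suspend it.
- They may decide to continue where the events are clearly not relevant to the remaining infusions, for example events confined to cocaine-only sessions before Day 3. No exemption may depend on treatment allocation.
- The IRB is notified if dosing is suspended, as 9.10 already requires.

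The text cost is two or three sentences, with no new committee. The operational cost arises only if a criterion is met. A held Day 8 or Day 9 session may be lost, because Sessions 4 and 5 are on consecutive days and Day 9 carries the last dose. Since a completer must finish all five sessions, that loses a completer against a margin of 2 per group, and replacement is blocked while the enrolment halt stands. A decision taking longer than 24 hours could cost more than one session.

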## 10 ASSESSMENT METHODS

### 10.1 Adverse Events

Reports of AEs will be elicited by a verbal probe (*e.g.*, “How are you feeling?”) administered starting with the first cocaine screening infusion on Day -2. Any events spontaneously reported by the participant or observed by the investigative staff will also be recorded. AEs will be assessed for severity and relationship to the study drug in accordance with the criteria in [APPENDIX B](#).

## 10.2 Urine Toxicology Test

A urine toxicology test will be administered at screening and intake to assess for the following drugs: alcohol, amphetamine/methamphetamine, barbiturates, benzodiazepines, buprenorphine, cocaine, fentanyl, MDMA, methadone, PCP, propoxyphene, THC, and opioids (*e.g.*, codeine, heroin, morphine, oxycodone, etc.).

## 10.3 Blood Sample Collections for Pharmacokinetic (PK) Determinations

An i.v. catheter will be inserted for each infusion session and may be maintained in place for the 2 days of infusion sessions in one week, if the participant wishes. PK blood samples will be obtained by either direct venipuncture or use of an indwelling catheter. If a catheter is used, two i.v. catheters will be placed for infusion sessions that involve repeated blood draws; one will be for cocaine administration, the other for blood sample collection.

Approximately 179 mL blood will be collected for PK analysis and other clinical tests ([APPENDIX A](#)). PK samples will be assayed for cocaine, BE, and SXC-2023 (as appropriate) using validated bioanalytical methods of liquid chromatography with tandem mass spectrometry (LC-MS/MS). For details of sample collection, processing, and shipment to the bioanalytical laboratory see the study Manual of Procedures (MOP).

### 10.3.1 Cocaine and BE

Blood samples (4 mL) will be collected during infusion Sessions 3 (Day 2) and 5 (Day 9) at pre-dose (approximately 15 minutes before the first infusion) and at 5, 15, 30, 65, 75, 90, 120, 150, and 180 minutes, and at 4, 8, and 12 hours after the first infusion.

Samples will be collected for assessment of cocaine and BE PK in 4-mL Vacutainer™ tubes containing K2EDTA.

### 10.3.2 SXC-2023 Blood PK

On Day 9, blood samples will be collected approximately 15 minutes prior to the morning dose and 1, 2, 3, 4, 6, 8, 12, 16, 24, 36, and 48 hours post-dose.

Samples for collection of SXC-2023 PK will be collected in 4-mL Vacutainer™ tubes containing sodium heparin.

## 10.4 Brief Substance Craving Scale (BSCS)

The BSCS is a self-administered assessment that asks the participant to rate his or her craving for cocaine. The BSCS used for this study is a modification of the State of Feelings and Cravings Questionnaire (Mezinskas *et al.*, 1998). Participants will use an electronic patient reported outcomes (ePRO) system provided by Technical Resources International, Inc., to answer BSCS. BSCS will be administered at pre-infusion and 125 minutes after the start of the cocaine infusion (Sessions 2 to 5).

## 10.5 Cardiovascular Assessments During Infusion Sessions

Before and after each i.v. infusion, the participant's physiologic responses will be closely monitored using repeated HR, BP, and ECG readings, assessed in semi-supine position.

During the Screening Infusion Session 1, BP and HR will be recorded at the following nominal time points relative to the first infusion of the day: -30, -15, 5, 10, 15, 20, 25, 30, 45, 55, 65, 70, 75, 80, 85, 90, 105, 115, 125, 130, 135, 140, 145, 150, 165, 180, 210, 240, 270, 300, 330 and 360 minutes. Out of range BP and HR collected during the first 180 minutes post-dose will be repeated if deemed necessary by an investigator. Continuous cardiac monitoring with telemetry beginning approximately 60 minutes before the first infusion until 4 hours after the last cocaine infusion. Twelve-lead ECG measurements will be recorded at -30 minutes and at 5, 10, 15, 30, 45, 65, 70, 75, 90, 105, 125, 130, 135, 150, 165, 180, and 360 minutes after the first infusion. Study personnel and staff will monitor participants for at least 1 hour after each infusion. Times for collection of ECG and vital signs are nominal times  $\pm 3$  minutes for the first 30 minutes after the infusion and  $\pm 5$  minutes at all other time points. ECG then vital signs will be collected first when multiple assessments are scheduled at the same nominal time.

During the baseline and treatment infusions (Sessions 2 to 5), BP and HR will be recorded at the following time points relative to the first infusion of the day: -30, -15, 5, 10, 15, 20, 25, 30, 45, 55, 65, 70, 75, 80, 85, 90, 105, 120, 150, 180, 210, 240, 270, and 300 minutes. Out of range BP and HR collected during the first 180 minutes post-dose will be repeated if deemed necessary by an investigator. Continuous cardiac monitoring with telemetry beginning approximately 60 minutes before the first infusion until 4 hours after the second infusion. Twelve-lead ECG measurements will be recorded at -30 minutes and at nominal 5, 10, 15, 30, 45, 65, 70, 75, 90, 120, 150, 180 and 300 minutes after the first infusion. Times for collection of ECG and vital signs are nominal times  $\pm 3$  minutes for the first 30 minutes after the infusion and  $\pm 5$  minutes at all other time points. ECG then vital signs will be collected first when multiple assessments are scheduled at the same nominal time.

ECG measurements to be recorded on a CRF include HR, RR, PR, QRS, and QT interval. For data analysis the QT interval will be corrected using the method of Fridericia (1920) (QTcF).

